10 METHODOLOGY

10.1 Screening examination - Visit 1

Screening examination will be performed prior to inclusion and prior to the first intended administration of the IMP to ensure that patients are eligible for the clinical trial.

The following assessments will be performed on Visit 1 (V1):

- demographic (age, sex, ethnic origin) and anthropometric data (body weight, height, BMI)
- medical history (including prior and concomitant medication)
- physical examination vital signs (blood pressure, pulse rate, body temperature (axillar))

Objective examination: skin and visible mucosa, palpation of abdomen and lymph nodes (submandibular, anterior and posterior cervical ones), oropharyngoscopy will be performed to assess the status of the tonsillitis.

Hence, objective symptoms included in the “Local Tonsillitis Manifestation Scale” are assessed using a 4-point rating scale using score “0” absent, “1” mild, “2” moderate, and “3” severe/pronounced. Diagnoses will be refined by using the Mclsaac Scale (see 0)

- clinical laboratory investigation: blood analysis including haematology, haemostatic system, serum chemistry, serology, urinalysis or other laboratory investigations are performed at the discretion of the investigator
- female status (in females with childbearing potential pregnancy test)

Finally, a self-assessment of the patient’s throat pain by him/herself and (or) his/her parent(s) using a visual analogue scale (VAS) is performed.

All data has to be documented by the investigator in the patient’s medical file and recorded in the CRF. Afterwards, inclusion and exclusion criteria are checked by the investigator, documented in the patient’s medical file, and recorded in the CRF.

At the end of Visit 1 the patient will be randomized, sorted to one of the two study groups and IMP will be handed over.

10.2 Status evaluation - Visit 2

The next status evaluation of the disease will be performed on day 3, i.e. ± 1 day after Visit 1 (V1).

A physical examination of vital signs (blood pressure, pulse rate, body temperature (axillar)) will be performed. All physical examinations done at V1 including skin and visible mucosa, palpation of abdomen and lymph nodes, oropharyngoscopy will be repeated to assess the status of the tonsillitis.

Again, objective symptoms included in the “Local Tonsillitis Manifestation Scale” are assessed and diagnoses will be refined by using the Mclsaac Scale (see 0).

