Checks for general well-being (AE-checks), checks of restrictions and medication will be performed.

The investigator will estimate indicators for prescription of antibiotics and will decide whether a patient will remain on the study treatment or not. If an antibiotic agent is prescribed, details will be documented and the patient will be instructed about the mode of administration. Intake of

antibiotic drug will be documented in the CRF. Patients with intake of antibiotics will be evaluated separately. At the discretion of the investigator the patient may be advised not to take IMP anymore. If so, this will be documented as well.

Self-assessment of the patient's throat pain by him/herself and (or) his/her parent(s) using a visual analogue scale (VAS) is performed afterwards. Moreover, forms for VAS assessment will be handed over to the patient. The patient will have to assess his/her sore throat every study day until visit 4 on study day 10±1.

10.3 Interim evaluation of treatment efficacy- Visit 3

Visit 3 (V3) will be performed on day 5 ±1 by a telephone call.

Intermediate evaluation of the effectiveness of treatment (day 5-day ±1) via telephone (or visit if necessary); patients self-assessment (VAS; 0-10)

10.4 Treatment efficacy, end of Reference treatment - Visit 4

At visit 4 (V4) on day 10 ±1 the status of the disease will be again evaluated.

A physical examination of vital signs (blood pressure, pulse rate, body temperature (axillar)) will be performed. All physical examinations done at V1 including skin and visible mucosa, palpation of abdomen and lymph nodes, oropharyngoscopy will be repeated to assess the status of the tonsillitis.

Again, objective symptoms included in the "Local Tonsillitis Manifestation Scale".

Checks for general well-being (AE-checks), checks of restrictions and medication will be performed.

Self-assessment of the patient's throat pain by him/herself and (or) his/her parent(s) using a visual analogue scale (VAS; 0-10 points) is performed. Forms of VAS assessment will be collected from the patient.

10.5 Treatment efficacy, end of treatment - Visit 5

Visit 5 (V5) will be performed on day 28 by a telephone call (for both the groups).

Checks for general well-being (AE-checks), checks of restrictions and medication will be performed.

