The FAS consists of all randomized patients with at least one documented application of IMP and with at least one observed post-baseline value.

Per Protocol Set (PPS)

The PPS consists of all patients of the FAS without major protocol deviations. The evaluation of protocol deviations and whether they lead to the exclusion of a patient from the PPS will be performed during data review of the study.

Primary endpoint

Main criterion for evaluation in the trial will be:

- Scores determined by the Local Tonsillitis Manifestations Scale refined by McIsaac's scale. Scores will be dichotomized to decide for two categories (therapy effective/therapy ineffective). Scores will be evaluated by treatment and time point, i.e. per visit
- Need for an antibacterial therapy, i.e. number of patients per treatment.

Secondary endpoints

- Scores/Intensity of each underlying disease symptom assessed by the Local Tonsillitis Manifestations Scale by treatment and time point, i.e. per visit
- Axillary temperature per treatment and measurement time point
- Patient's self-assessments on VAS per treatment and measurement time point
- Self-assessment of the symptoms by the patient.

Safety evaluation

AEs will be evaluated considering frequency and intensity. Furthermore, AEs will be evaluated considering relationship to the IMP, outcome, and seriousness. Both will be described by absolute and relative frequency. Descriptive statistics will be calculated for clinical laboratory parameters determined. Frequencies of values inside and out of normal range (i.e. above and below) will be given where possible.

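### At Visit 2 the throat-pain VAS is rated after the antibiotic decision, so an open-label secondary endpoint can be influenced by a decision that may differ by arm (minor)

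*Protocol*

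**What the plan says.** Protocol section 10.2 describes Visit 2 in this order: physical examination, the objective LTM symptoms and the McIsaac scale, adverse-event and medication checks, then the treatment decision. On the decision it says: "The investigator will estimate indicators for prescription of antibiotics and will decide whether a patient will remain on the study treatment or not". It continues: "If an antibiotic agent is prescribed, details will be documented and the patient will be instructed about the mode of administration". It also says: "At the discretion of the investigator the patient may be advised not to take IMP anymore", and of antibiotic takers: "Patients with intake of antibiotics will be evaluated separately". The next paragraph turns to the self-assessment of throat pain, by the patient and/or a parent, which "using a visual analogue scale (VAS) is performed afterwards". In the sentence after that, "forms for VAS assessment will be handed over to the patient" for daily rating until Visit 4.

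At Visit 1 (section 10.1) the VAS comes before allocation: "At the end of Visit 1 the patient will be randomized".

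Section 8.4 states that there is no blinding. Protocol section 12.2.3 and the SAP both list as a secondary endpoint: "Patient's self-assessments on VAS per treatment and measurement time point". The need for antibacterial therapy, by treatment, is part of the main criterion (section 12.2.2 and the SAP).

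**The concern.** A pain rating given by someone who knows the arm is already open to expectation. Section 10.2 adds a second, avoidable influence: before rating, the family may have learned whether the child will get an antibiotic or should stop the study drug. Section 6.1 itself separates the family's wish to be rid of pain from the doctor's judgement about antibiotics, so the protocol recognises that expectation matters here.

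If prescribing differs by arm, any effect of hearing the decision on the rating enters the Visit 2 arm comparison. It could not be separated afterwards, because section 10.2 schedules no VAS between Visit 1 and the decision. The synopsis asks for daily self-assessment but gives no start day, so it does not clearly supply an earlier rating.

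**Working it through.** **Order of events.** The word placing the VAS after the decision is explicit in section 10.2. Section 8.5 lists the Visit 2 items with antibiotic need named before the LTM scale and the VAS. It is a list without a stated sequence, so it neither contradicts nor independently confirms section 10.2.

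**The plan's own figures.** The documents give no figure for the VAS: no expected difference, SD or power. The sample size in the synopsis is for the dichotomous main variable and reproduces: (1.96 + 0.84)² × (0.75 × 0.25 + 0.90 × 0.10) / 0.15² = 7.84 × 0.2775 / 0.0225 = 96.69, so 97 per arm, and 97 / 0.97 = 100. This point does not dispute it. Only the 100 per arm and the 75% and 90% success rates are used below.

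**Size of the shift, on assumptions.** If hearing that an antibiotic is prescribed moves the rating by the same amount in both arms, then:

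shift in arm difference = (arm difference in share prescribed) × (rating shift)

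- Prescribing difference: 0 to 15 points (assumed). The upper end treats every failure in the sample-size table as a prescription: 25% − 10% = 15 points. The documents do not say this.
- Rating shift: 0 to 2 points on 0-10 (assumed, in either direction).

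| Prescribing difference | Shift 0 | Shift 0.5 | Shift 1 | Shift 2 |
|---|---|---|---|---|
| 0 | 0 | 0 | 0 | 0 |
| 0.05 | 0 | 0.025 | 0.05 | 0.10 |
| 0.10 | 0 | 0.05 | 0.10 | 0.20 |
| 0.15 | 0 | 0.075 | 0.15 | 0.30 |

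**Against the precision of the trial.** With SD 2 (assumed) and 100 per arm, SE = 2 × √(2/100) = 0.283, and the difference detectable with 80% power is 2.80 × 0.283 = 0.79 points. For SD 1.5 to 3 it is 0.59 to 1.19. At SD 2, if prescribing differs but pain before the decision does not, shifts of 0.075, 0.15 and 0.30 would raise a nominal 5% two-sided error to about 5.8%, 8.3% and 19%.

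**If antibiotic takers are analysed separately.** Among the remaining patients everyone has had the same decision, and among takers a common shift cancels between arms. By this route the shift then falls towards 0. The documents do not define how separate evaluation is to be done.

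**Advice to stop the study drug.** This route can operate only in the Imupret arm. It would add (share advised to stop) × (shift from that advice). The documents give neither term, so it is outside the 0 to 0.30 range.

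**The case against.** The strongest case against acting has four parts.

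- Families know their arm from Visit 1, and under the delayed-prescription concept in section 6.1 a prescription is already written. Expectation about antibiotics therefore exists before Visit 2. This stands: reordering removes only the added effect of hearing the decision.
- Every later VAS is rated with that knowledge too, and possibly on an antibiotic. This stands: only one time point is protected.
- A rating made before the decision is not neutral either, since a parent who wants or fears an antibiotic could rate accordingly. This is possible, but that rating would still describe the child before the decision, which the present order does not provide.
- The shift, its direction and the SD are all assumed, and the plan intends to evaluate antibiotic takers separately. This stands, and is why the range starts at 0. Separate evaluation has its own weakness, because it conditions on an event after randomisation. That is a different issue.

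A reader might infer more than the documents support. That the antibiotic decision does differ by arm is the trial's first question (sections 6.3 and 7), not a stated fact. That every family has the decision explained before rating is also not stated: instruction is described only where an antibiotic is prescribed. Nor can one conclude that the main criterion is contaminated. The objective LTM items come before the decision in section 10.2. The place of the subjective complaint items is not stated, so an effect on them is neither shown nor excluded.

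**Conclusion.** The point holds as a minor weakness in measurement order. Section 10.2 places the Visit 2 VAS after the antibiotic and stay-on-treatment decision, in an unblinded trial where that VAS is a secondary endpoint, and it schedules no earlier post-baseline rating. The rating can be influenced by a decision that may differ by arm.

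The size is unknown and probably small: 0 to 0.30 points in the pooled arm comparison, on an assumed prescribing difference of 0 to 15 points and an assumed common rating shift of 0 to 2 points. It is 0 if prescribing is equal and the shift is the same in both arms. The 0.30 is the end of an assumed range, not an estimate of bias. The finding concerns one time point of one secondary endpoint in a trial that both documents call exploratory. It does not invalidate the VAS comparison as a whole.

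**What to change.** Change the measurement order only; the decision itself is untouched.

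1. In section 10.2, move the VAS to the start of Visit 2, so that the patient and/or parent completes it before the antibiotic decision is made or discussed.
2. State in section 10.2 that the subjective LTM complaint items are also scored before that point.
3. Record who made the rating and at what time, and the time of the decision.
4. Put the Visit 2 items in section 8.5 in the same order, and state the day on which daily VAS rating begins, which the synopsis leaves open.

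The cost is one reordered paragraph, a matching edit to section 8.5 and the synopsis, and a few fields on the CRF page. No procedure is added. General open-label bias and the later ratings remain as they are, and the report should say so.

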5 TRIAL SYNOPSIS

Trial code	ATi-2
Title of Trial	A Protocol of a Multicenter, Randomized, Open-Label, Comparative Study of Therapeutic Efficacy, Safety and Tolerability of Imupret application in the therapeutic concept of delayed prescription of antibiotics in children, aged 6-12 with severe acute tonsillitis.
Working title	Imupret in tonsillitis
Trial Design	open-label, exploratory, comparative, multicentre, randomized, prospective, parallel-group study.
Clinical phase	IV
Inclusion diagnosis	Acute tonsillitis
Trial objectives	
Assessment of the influence of Imupret (drops) prescriptions in the therapeutic concept of delayed prescription of antibiotics to:
 
 • need for antibiotics • regression of the tonsillitis symptoms • duration of antipyretics administration
Number of patients	approximately N=200 (1:1 ratio active treatment: reference)
Specialization of investigator	Head of Department of Otorhinolaryngology Head & Neck Surgery
Time schedule	Planned FPI (First patient in): approximately February 2019 Planned LPO (Last patient out): approximately December 2019
Efficacy endpoints	
The main criterion (main variable):
 
 - decrease in the severity of each symptom (complaint) that is part of the Mclsaac scale of tonsillitis manifestations, up to 1 point or less. This variable is dichotomous, with the categories "treatment effective" and "treatment not effective": - Treatment is effective - reducing the severity of each symptom (complaint) that is part of the Local Tonsillitis Manifestation Scale (0-15), of tonsillitis manifestations, up to 1 point or less in the evaluation stages. Absence of indications for prescribing antibacterial therapy - Treatment is not effective - the condition given for the category "therapy is effective" is not met.
Secondary end-points	
Secondary variables:
 
 - a decrease in the severity of the symptoms of the underlying disease, at the 2- nd, 3 -rd and 4- th visits compared to the 1- st visit. - decrease in the total score (the sum of scores for each symptom) according to the scale of local manifestations of tonsillitis at the 2-nd, 3-rd and 4-th visits in comparison with the 1-st visit. - a decrease in temperature in the armpit at the 2-nd and 3-rd visits compared to the 1-st visit. - a patient's self-assessment of the quality of life (every day). - Duration of NSAID administration. -Therapy compliance

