Safety evaluation	
 - Adverse events (AEs), serious adverse events (SAEs) - Incidence of adverse drug reactions (ADRs)

	
- Overall assessment of tolerability
												

Methodology
	
 1. Medical history, demographic and anthropometric data at screening. 2. Complaints, patient questioning by organs and systems – at each visit, including any unscheduled visit and telephone contact. 
All complaints are assessed using a 4-point rating scale, beginning from the visit at which the complaint was identified for the first time.
 
 3. Physical examination: skin and visible mucosa examination, palpation of abdomen and lymph nodes, oropharyngoscopy are performed at each visit including any unscheduled visit. 
Symptoms are assessed using a 4-point rating scale, beginning from the visit at which the symptom was identified for the first time.
 
 4. Evaluation of probability of acute bacterial tonsillitis in accordance to McIsaac scale (sum of scores) 
  
 McIsaac scale (sum of scores)	The probability of the identification of β-hemolytic streptococcus in a smear from pharynx	
   
 -1 or 0	1%	
 
 1	10%	
 
 2	~17%	
 
 3	~35%	
 
 4 or 5	~50%	
  
 
 5. Complaints included in the Local Tonsillitis Manifestations Scale are assessed at each visit including any unscheduled visits 6. Symptoms included in the Local Tonsillitis Manifestations Scale are assessed at each visit 7. Axillary temperature assessment at each visit including any unscheduled visits. 8. Clinical blood count, urinalysis and blood chemistry according to the investigator's decision. 9. Self-assessment of the patient's state of health by him/herself and (or) his/her parents using a visual analogue scale is performed on a daily basis. 	McIsaac scale (sum of scores)	The probability of the identification of β -hemolytic streptococcus in a smear from pharynx	-1 or 0	1%	1	10%	2	~17%	3	~35%	4 or 5	~50%

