10.6 Clinical assessments and parameters

Assessment of tonsillitis will be performed according to the Local Tonsillitis Manifestation Scale. In detail the following symptoms will be investigated:

Local Tonsillitis Manifestation Scale

- Sore throat at swallowing (0 – absent, 1 – mild, 2 – moderate, 3 – severe / pronounced);
- Sore throat at rest, i.e. during the intervals between swallowing acts (0 – absent, 1 – mild, 2 – moderate, 3 – severe / pronounced);
- Throat irritation at rest, i.e. during the intervals between swallowing acts (0 – absent, 1 – mild, 2 – moderate, 3 – severe / pronounced);
- Cough associated with throat discomfort (0 – absent, 1 – mild, 2 – moderate, 3 – severe / troublesome).
- Posterior pharyngeal wall hyperaemia (0 – absent, 1 – mild, 2 – moderate, 3 – severe / pronounced);
- Palatine tonsils hyperaemia (0 – absent, 1 – mild, 2 – moderate, 3 – severe / pronounced);
- Palatine tonsils oedema (0 – absent, 1 – mild, 2 – moderate, 3 – severe / pronounced).

Diagnoses will be further refined using the Mclsaac Scale

Symptom	Score
Body temperature exceeding 38°C	+1
Absence of cough	+1
Painful anterior cervical lymph nodes	+1
Tonsillar oedema and/or exudate on tonsils	+1
Age 3–14 years old	+1
15–44 years old	0
>45 years old	- 1

Assessment of type of tonsillitis:

Score 0 – probability of group A β -haemolytic streptococcus (GABHS) infection is 1-2%;

Score 1 – probability of GABHS infection is 5-10%;

Score 2 – probability of GABHS infection is 11-17%;

Score 3 – probability of GABHS infection is 28-35%;

Score 4 – probability of GABHS infection is 51-53%;

Self-assessment of the quality of life by the patient.

- Sore throat at swallowing (0 –10 points VAS);
- Sore throat at rest, i.e. during the intervals between swallowing acts (0 –10 points VAS);
- Throat irritation at rest, i.e. during the intervals between swallowing acts (0 –10 points VAS);
- Cough associated with throat discomfort (0 –10 points VAS).

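### Take-home VAS forms are first handed out at Visit 2, so the daily self-assessment endpoint is not collected on the day or days between Visit 1 and Visit 2

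*Protocol*

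**What the plan says.** The synopsis lists among the secondary endpoints "a patient's self-assessment of the quality of life (every day"), and item 9 of its Methodology row says that self-assessment "using a visual analogue scale is performed on a daily basis".

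The visit sections describe something narrower:

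- **Section 10.1 (V1, day 1):** one "self-assessment of the patient’s throat pain by him/herself" or by a parent is done at the visit. At the end of the visit the child is "sorted to one of the two study groups and IMP will be handed over". Forms are not mentioned.
- **Section 10.2 (V2):** after the V2 rating, "Moreover, forms for VAS assessment will be handed over to the patient". The instruction to rate every day up to Visit 4 (V4) stands in the same paragraph and nowhere earlier.
- **Section 10.4 (V4, day 10±1):** the completed forms are collected.
- **Section 8.5:** V2 is on day 3±1. Self-assessment is listed at V1, V2, V3 and V4, with no home diary between V1 and V2.

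The instrument also goes by several names. It is quality of life in the synopsis endpoint list and in section 10.6 ("Self-assessment of the quality of life by the patient"), state of health in synopsis item 9, and throat pain in sections 10.1, 10.2 and 10.4. Section 10.6 shows what it contains: four 0–10 symptom items, three on the throat and one on cough.

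**The concern.** A daily endpoint needs a means of recording from the first day. Here the means arrives at V2, so a site that follows the visit sections exactly cannot deliver what the synopsis promises.

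The days lost are relevant to the trial's aims. The second question in section 6.3 is whether Imupret, taken in the acute period, speeds the regression of symptoms. The unrecorded days are the first home days on treatment, and they come before V2, when the protocol first schedules a decision on antibiotics. Sections 8.3.3 and 10.2 evaluate children who take antibiotics separately, so later diary days are divided by an event that occurs after randomisation. Daily ratings taken before that decision would not be divided in this way.

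The labelling is a lesser matter. Four symptom ratings do not measure quality of life, and the varying names leave it unclear whether the daily form carries one item or four.

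**Working it through.** The documents state no figure for diary coverage, so there is none to reproduce. The check is a count of days.

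**Inputs.** V1 is day 1, V2 is day 3±1 (day 2, 3 or 4) and V4 is day 10±1 (day 9, 10 or 11), all from section 8.5. A clinic VAS is taken on the V1 day (section 10.1) and on the V2 day (section 10.2). Home forms are available from V2 (section 10.2).

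**Formula.** Only days strictly between V1 and V2 lack a source:

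days without a rating = V2 day − V1 day − 1 = V2 day − 2.

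| V2 held on | Days without a rating | Share if V4 is on day 10 | Share if V4 is on day 9 to 11 |
|---|---|---|---|
| Day 2 | none | 0/10 = 0% | 0% |
| Day 3 (nominal) | day 2 | 1/10 = 10% | 1/11 to 1/9 = 9% to 11% |
| Day 4 | days 2 and 3 | 2/10 = 20% | 2/11 to 2/9 = 18% to 22% |

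**Consequence for the summaries.** Section 12.2.3 and the SAP summarise VAS by treatment and time point. If study day is the time point, the children who contribute are:

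- day 2: only those whose V2 was on day 2;
- day 3: those whose V2 was on day 2 (home form) or day 3 (clinic rating);
- day 4 onwards: all children, apart from ordinary missing entries.

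The day-2 and day-3 summaries would therefore describe subsets chosen by visit date. The documents do not say how V2 dates will be distributed, so the size of those subsets cannot be given.

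**After the change.** With forms handed out at V1, the count falls from V2 day − 2 (0, 1 or 2) to 0 for every V2 date. No sample size or power figure depends on this.

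**The case against.** The strongest reply is that little is lost. At the nominal schedule one day is missing, and it lies between ratings at V1 and V2, so early change is measured in both arms. The Local Tonsillitis Manifestation Scale and axillary temperature are also recorded at both visits. VAS is a secondary endpoint in a trial that calls itself exploratory, and no VAS slope, area under the curve or time to resolution is specified. Nothing in the protocol makes V2 timing differ by arm. Section 10.1 is merely silent about forms, and the synopsis already requires daily rating. Nor do the analysis sections speak of quality of life: section 12.2.3 and the SAP refer to self-assessments on VAS and of symptoms.

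Most of this stands, and it limits the size of the point. The appeal to silence does not. Section 10.2 expressly places both the hand-over and the daily instruction at V2, and a site works from the visit sections. The missing days cannot be recovered afterwards.

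A reader might also infer more than the documents support:

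- **That the gap covers the steepest part of the illness.** Neither document gives a day-by-day symptom course, so this would be an outside assumption.
- **That it is the only antibiotic-free stretch.** Children not prescribed an antibiotic at V2 remain free of antibiotics afterwards, with daily forms. Conversely, section 6.1 describes starting antibiotics if there is no effect within 36–48 hours, and section 8.5 allows unscheduled visits on worsening, so antibiotics could begin before a V2 held on day 4.
- **That before V2 the arms differ only by Imupret.** The trial is open-label, and both arms may use paracetamol and topical agents as needed from the start.

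**Conclusion.** The point holds as an internal conflict with a small, definite effect. As written, the daily VAS endpoint has no source on day 2 at the nominal V2 date, on days 2 and 3 if V2 is on day 4, and on no day if V2 is on day 2: 0 to 2 of 10 study days, nominally 1. What is lost is the daily course between V1 and V2, before the first scheduled antibiotic decision. The overall V1-to-V2 change is kept. The missing days vary between children with the V2 date, but the documents give no reason to expect them to vary by arm, so there is no basis for claiming a biased treatment comparison.

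This rests on two assumptions: that sites follow sections 10.1 and 10.2 literally, and that a clinic rating counts as that day's rating. If sites handed out forms at V1 on the strength of the synopsis, the gap would close, but the protocol does not tell them to.

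The naming of the instrument is a minor wording matter. The objectives plan no quality-of-life claim.

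**What to change.** In section 10.1, hand out the VAS forms at V1 together with the instruction to rate every day. Collect ratings from day 1 to V4, with the V1 clinic rating serving as the day-1 entry. Move or repeat the daily instruction accordingly, remove the first hand-over from section 10.2, and add the home diary to section 8.5, so that these sections agree with the synopsis.

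As a minor accompanying change, use the four items of section 10.6 at every rating. Call the endpoint patient-rated throat symptoms (VAS) in the synopsis and section 10.6, and align the other names in synopsis item 9 and sections 10.1, 10.2 and 10.4.

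The cost is one extra home entry per child at the nominal V2 date, two if V2 is on day 4 and none if it is on day 2, plus the text edits. Visits, sample size and treatment are unchanged.
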